## **Study Protocol**

The proposed study will examine the question of whether phobic individuals will use a mobile phone in self-directed exposure therapy. A second question is whether phobic participants will find the use of a mobile phone as an acceptable means of conducting self-directed exposure therapy.

Accompanying these two research questions are additional specific hypotheses. The first hypothesis is that filmed exposure stimuli, available on a mobile phone, will be associated with greater fear reduction in a self-directed exposure group relative to a control group. The second hypothesis is that greater presence will be reported with first-person perspective versus third-person perspective.

## **Method**

### **Experimental Design**

A three-group by two-assessment mixed prospective design will be used in this study. Participants will be randomly assigned to the order of each group and condition. See *Figure 1* for flowchart of the proposed study.

### **Participants**

G\*Power 3, a power analysis program, developed by Faul, Erdfelder, Lang, and Buchner (2007), was used to determine sample size. In order to achieve a power of  $\phi = .80$  with two measurements and three groups at a medium effect size of .25, the analysis suggests a total sample size of at least 36 participants. Inclusion for participation will include fluency in the English language, being 18 years of age or older, own or have access to a mobile phone, and report discomfort with dental related care. The participants will receive a compensation of \$40.00 upon completion of the study. This study will adhere to the guidelines presented by the

American Psychological Association for treatment of human research participants. In order to participate, subjects will be required to sign an informed consent statement that will be approved by the West Virginia University Institutional Review Board.

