### **Procedure**

The participants in the study will be recruited through advertisements in local newspapers, posted flyers on the campus of West Virginia University, and advertised on Craigslist (e.g., a website that provides services/goods). Upon arrival to the study, participants will be given a written informed consent form and information on study procedures. The researchers will discuss the process of the study and what is expected of the participant. The participants will be informed that they will receive \$40.00 for compensation at the completion of the study. After agreement to enlist in the study and completion of the ADIS-5, the participants will be randomly assigned to group (i.e., 2-week waitlist or treatment group) by previously prepared sealed opaque envelopes, complete the demographic questionnaire, conducted the DBAT, and answer the DFS. The researchers will then provide a 15-minute demonstration on how to conduct self-directed exposure therapy on the participant's mobile phone, and how to rate

SUDS. The researchers will describe that watching the exposure video three times per day is the ideal, one time per day is the suggested minimum, and viewing the exposure video five times per day is the suggested maximum.

The video will display a typical preventive visit to the dentist, including walking into the dental office, being called back for treatment by the dental assistant, sitting in the dentist chair, and seeing the dentist perform a teeth cleaning. The video will be 15-minutes in length, and be recorded by the researchers in both first- and third-person perspective. The actors in the video will be confederates and have knowledge about the purpose of the video. The actors in the video are from the School of Dentistry at West Virginia University.

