Proposed Analyses

Rates of procedure adherence (i.e., watching the video at least three times daily) will be assessed in order to examine the study's first question. The second question will be assessed by examining participants' rating of acceptability on the AARP with using a mobile phone as a method for self-directed exposure.

There will be 3 (group) x 2 (assessment) mixed measures analyses of variance (ANOVAs) which will be conducted to assess the first hypothesis regarding treatment effectiveness, with the DFS, and various DBAT measures (i.e., avoidance/escape, cardiac response, and SUDS verbal reports) as dependent variables. Sensitivity analyses will be conducted for baseline measurements. In order to examine the second hypothesis, a paired sample *t*-test assessing the relation of video perspective and scores on the PQ will be conducted.

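### The basis for N=36 is not stated: under ordinary inputs 36 fits the time main effect, while the interaction that tests Hypothesis 1 has power of about .73, and only for a difference in change of about 1.06 SD

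*Protocol*

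**What the plan says.** The Participants section of the protocol reports a G*Power calculation for power of .80 "with two measurements and three groups at a medium effect size of .25", and concludes that "the analysis suggests a total sample size of at least 36 participants". No other input is given.

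The Experimental Design section states that "A three-group by two-assessment mixed prospective design will be used in this study". The opening section gives Hypothesis 1: filmed exposure on a phone "will be associated with greater fear reduction in a self-directed exposure group relative to a control group". The SAP assesses that hypothesis as follows: "There will be 3 (group) x 2 (assessment) mixed measures analyses of variance (ANOVAs", "with the DFS, and various DBAT measures" as dependent variables.

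Under Procedure, participants are first "randomly assigned to group (i.e., 2-week waitlist or treatment group"; the treated participants are then randomised to which video perspective they see first. No allocation ratio is given at either step. The only correlation in the documents is the DFS test-retest value of .88, under Self-Report Measures; it is not linked to the power calculation.

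**The concern.** Hypothesis 1 concerns a difference between groups in how much fear falls. In a 3 x 2 mixed ANOVA that is the group x assessment interaction. A sample size for this design can instead be computed for the time main effect or the between-groups effect, and the three give very different answers. The protocol does not say which was used.

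The label also needs care. An f of .25 is conventionally called medium, but for an interaction with two assessments its meaning depends on whether f is scaled to the raw SD or to the SD of change. The documents never convert .25 into a difference on the DFS or on any Dental Behavior Avoidance Test (DBAT) measure.

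What is at stake is how a null result is read. Someone relying on the Participants section could take a non-significant Hypothesis 1 test as evidence against a medium benefit. At moderate correlations the design would usually miss such a benefit.

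**Working it through.** **Inputs from the documents:** 3 groups, 2 assessments, effect size .25, power .80, N = 36.

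**Assumptions, because the documents are silent:** Cohen's f; alpha .05 (.10 also tried); correlation rho = .5 (.3 to .88 also tried); 12/12/12 allocation (18 waitlist/9/9 also tried); N rounded up to a multiple of 3; no dropout.

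**Step 1: reproduce 36.** With f on the raw SD, the noncentrality is lambda = f² × N × 2/(1 − rho). At N = 36 and rho = .5 this is .0625 × 36 × 2/.5 = 9.0.

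- Time main effect, df (1, 33): power .829. At N = 33 lambda is 8.25 and power .794. So N = 36 reproduces.
- Group x assessment interaction, df (2, 33): power .729. At N = 42 lambda is 10.5 and power .803. So the interaction needs 42.

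Three other routes give 36 for the interaction:

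- raw-SD f with rho of about .58 to .61 (for example, .826 at rho = .60);
- raw-SD f with rho = .5 and alpha .10 (.830);
- .25 read as a partial eta-squared, so f² = .25/.75 = .333 and lambda = f² × (N − 3) = 11.0 (power .817 at 36, .772 at 33).

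Two routes fail. The between-groups effect at rho = .5 needs 120. With f = .25 on the SD of change the interaction needs 159, and power at 36 is .23 (lambda = f² × N = 2.25) or .21 (lambda = f² × (N − 3) = 2.06).

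**Step 2: what .25 means on each route.** With two assessments the interaction is a one-way ANOVA on change, with lambda = N × Var(mean changes)/[2 × SD² × (1 − rho)]. Setting this equal to f² × N × 2/(1 − rho) gives an SD of the mean changes of 2f = 0.50 raw SD, whatever rho is.

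- Two equal exposure orders against waitlist, 12/12/12: an exposure-waitlist difference D has SD of D × √(2/9) = .4714 D, so D = .50/.4714 = 1.06 raw SD.
- Allocation 18/9/9: D = .50/.50 = 1.00.
- Three equally spaced means: the range between extreme groups is 1.22.
- Partial eta-squared of .25: f = .577, so D = .577/.4714 = 1.22 SD of change.
- Time main effect: the same algebra gives an average pre-post change of 0.50 SD over all groups combined, waitlist included. It says nothing about a difference between groups.

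By the usual two-group benchmarks (0.5 SD medium, 0.8 SD large), every interaction route to 36 targets a difference above large.

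**Step 3: power at N = 36 for a 0.5 raw-SD difference in change.** With 12 per group, lambda = 36 × (2/9) × D²/[2(1 − rho)] = 4D²/(1 − rho). For D = 0.5 and rho = .5 this is 2.0. For the last column, power .80 on df (2, 33) needs lambda = 10.57, so D = √[10.57 × (1 − rho)/4].

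| rho | Power at 0.5 SD | Power at 0.8 SD | Difference detectable with power .80 |
|---|---|---|---|
| .3 | .16 | .35 | 1.36 SD |
| .5 | .21 | .48 | 1.15 SD |
| .7 | .33 | .70 to .71 | 0.89 SD |
| .88 | .69 | .98 | 0.56 SD |

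Pooling the two exposure orders against waitlist (24 v 12, t-test on change) gives .28 at rho = .5 and .80 at rho = .88 for a 0.5-SD difference.

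**The case against.** Four points can be made for the plan.

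1. An f of .25 is the standard medium value for Cohen's f, so the label follows convention. The 1.06 SD depends on a pattern of means and an allocation that the documents do not give. This stands as far as it goes: the label is not an arithmetic error. But the alternatives tried give 1.00 and 1.22 SD, so the conclusion does not turn on the pattern.

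2. Power depends on the correlation. At .88, raw-SD f = .25 has power above .99 at N = 36, and a 0.5-SD difference has .69 on the omnibus test or .80 on the pooled contrast. This stands for the DFS and limits the point. However, .88 is a test-retest reliability, which need not hold over two weeks in which some participants are treated. No correlation is given for the DBAT outcomes, and the SAP names no pooled contrast, although the wording of Hypothesis 1 would suit one.

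3. The sponsor's calculation cannot be identified. A reader might infer that the trial was sized on the wrong effect, or that 36 was obtained by targeting a 1.06-SD difference. The documents support neither. Several sets of inputs give 36, and 1.06 SD describes the interaction, not the time main effect that gives 36 under the ordinary inputs.

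4. No passage says that a non-significant result will be read as absence of a medium effect. That is right; the risk lies in how a reader would use the stated power.

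**Conclusion.** The point holds in a conditional form. The power statement lacks the inputs needed to check it, and none of the routes found to 36 gives .80 power for a medium exposure-waitlist difference on the planned Hypothesis 1 test. With raw-SD f, alpha .05 and correlation .5, the interaction has power of about .73 at 36 and needs 42, and f = .25 there is a difference in change of about 1.06 SD (12/12/12, equal orders). For a 0.5-SD difference, omnibus power runs from .16 to .69 over correlations of .3 to .88.

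A reader might go further and say flatly that the trial is not powered for a medium effect. The documents do not support that for the DFS: if its correlation stays near .88, the detectable difference is 0.56 SD. They do not support the contrary assurance either, for the DFS at lower correlations or for the DBAT measures. The fault is an under-specified power claim that reads more favourably than the planned test warrants. It should be corrected, but it does not invalidate the design.

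**What to change.** In the protocol's Participants section:

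- State the effect tested (group x assessment interaction), alpha, the assumed correlation between assessments, the effect-size metric and the allocation.
- Replace the claim of .80 power at a medium effect with the power that 36 participants give for that interaction. If the correlation is taken as .5, with alpha .05, raw-SD f and 12 per group, this is about .73 at f = .25, that is, a difference in change of about 1.06 SD between exposure and waitlist when both orders are equal.
- Give the differences detectable with power .80: about 1.15 SD at correlation .5, 0.89 SD at .7 and 0.56 SD at .88.

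In the SAP, state that the Hypothesis 1 difference in change will be reported with its 95% CI, and that a non-significant result will not be read as absence of a medium effect.

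The cost is wording only, with no change to enrolment. The downside is that the stated sensitivity becomes less favourable.

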### **Anxiety and Related Disorders Interview Schedule for DSM-5-Adult Version**

**(ADIS-5).** The ADIS-5 is a structured interview conducted by trained professionals that diagnosis current DSM-5 anxiety disorder, however, only the specific phobia section will be used in this study. Previous versions (i.e., ADIS, ADIS-R, & ADIS-IV) have demonstrated good psychometric properties (Brown, Di Nardo, Lehman, & Campbell, 2001; Di Nardo, Moras, Barlow, Rapee, & Brown, 1993). For the current study, The ADIS-5 will be conducted by clinicians in training, and be used in order to describe the study's sample.

**Subjective Units of Distress Scale (SUDS; Wolpe, 1973).** The SUDS is a visual analog scale in which the participants rate their anxiety/fear based on a range between 0 (*no anxiety/fear*) and 100 (*very severe anxiety/fear*). Refer to appendix B. A SUDS rating will be collected at the end of each video segment, reflecting maximum distress experienced during the viewing. An average of maximum distress ratings will be calculated for all segments viewed at a single time.

**Dental Fear Survey (DFS; Kleinknecht, Klepac, & Alexander, 1973).** The DFS consists of 20 self-report items that measure anxiety in regard to dental situations. Refer to appendix C. The measure examines physiological and behavioral responses to specific dental circumstances and situations, and contains three subscales. The subscales assess dental avoidance and anxiety, fear of dental stimuli/procedures, and arousal associated with dental

treatment. The DFS is rated on a 5-point Likert-type scale assessing how much of the responses (i.e., behavioral & physiological) occur in dental situations or the level of anxiety felt within the specific situations. The DFS has a total score of 100, and higher scores reflecting more anxiety felt with dental care-related fear (Kleinknecht et al., 1973).

DFS scores reflect general dental care-related fear and anxiety. The DFS has been widely utilized in behavioral dentistry research due to low demand on the participant in regard to time and cognitive requirements. The specific situations allow for individually measuring the participants' dental care-related fears. Furthermore, the DFS has demonstrated reliability (test-retest  $r = .88$ ) and validity ( $\alpha$ 's ranging from 75 to 95; McGlynn, McNeil, Gallagher, & Vrana, 1987; Smith & Moore, 1995; Heaton, Carlson, Smith, Baer, & Leeuw, 2007).

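### The stated power of .80 at 36 participants gives no alpha, no correlation and no effect powered; at alpha .05 and correlation .5 it fits the time main effect, while the group x assessment interaction has about .73 and needs 42

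*Protocol*

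**What the plan says.** The protocol (Participants) reports a G*Power 3 calculation for power .80 "with two measurements and three groups at a medium effect size of .25" and concludes that "the analysis suggests a total sample size of at least 36 participants". It does not state alpha, the correlation between the two assessments, the effect-size option, or whether the calculation was for the between-group effect, the within (time) effect or their interaction. The SAP adds none of these.

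Hypothesis 1 (protocol, opening section) is that filmed exposure on a mobile phone "will be associated with greater fear reduction in a self-directed exposure group relative to a control group". The SAP (Proposed Analyses) plans "3 (group) x 2 (assessment) mixed measures analyses of variance (ANOVAs) which will be conducted to assess the first hypothesis", with the DFS and the DBAT measures (avoidance/escape, cardiac response, SUDS) as outcomes. It does not say which F-test in that ANOVA decides the hypothesis.

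The only correlation in the documents that could bear on the calculation is in the description of the DFS, which says that "the DFS has demonstrated reliability (test-retest" r = .88). It is not offered as an input to the sample size.

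**The concern.** Hypothesis 1 concerns a difference between groups in change. In a 3 x 2 mixed ANOVA the omnibus term for that is group x assessment, with 2 numerator degrees of freedom. The assessment main effect asks only whether scores change on average over all groups. It could be significant if the waitlist improved as much as the exposure groups, so it says nothing about exposure versus control.

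A sample-size routine for this design returns different totals for the three effects. If the total was taken from the time effect, the .80 does not belong to the test that the plan relies on. A null result on Hypothesis 1 would then be read against a power figure which that test does not have. Because the protocol does not name the effect or the inputs, a reader cannot tell whether this happened.

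**Working it through.** **Inputs from the documents:** N = 36, power .80, k = 3 groups, m = 2 measurements, effect size .25 (protocol, Participants).

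**Assumed, because not stated:** the effect size is Cohen's f; alpha = .05; correlation between assessments rho = .5; equal thirds; no dropout. Alpha and rho are varied below.

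**Formulas** (noncentral F, G*Power default repeated-measures metric):
- Within effect and interaction: lambda = f² × N × m / (1 − rho).
- Time main effect: df = m − 1 = 1 and (N − k)(m − 1) = N − 3.
- Group x assessment: df = (k − 1)(m − 1) = 2 and N − 3.
- Between-group effect: lambda = f² × N × m / (1 + (m − 1) rho), df = 2 and N − 3.

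**Reproducing the stated 36.** At N = 36, lambda = .0625 × 36 × 2 / .5 = 9.0.

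| Total N | Time main effect, F(1, N−3) | Group x assessment, F(2, N−3) |
|---|---|---|
| 33 | .794 | .685 |
| 36 | .829 | .729 |
| 39 | .860 | .769 |
| 42 | .885 | .803 |

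The time main effect first reaches .80 in equal thirds at 36, which matches the protocol. The interaction has the same lambda of 9.0 but 2 numerator df. Its critical value is F(2,33) = 3.28, and its power is .729, so beta is 1 − .729 = .27 rather than .20. It first reaches .80 at N = 42 (lambda = .0625 × 42 × 2 / .5 = 10.5). The between-group effect needs 120. The two other effect-size conventions tried (SPSS-type and Cohen-type noncentrality) need 129 to 162 depending on the effect, so neither gives 36.

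**Dependence on the correlation** (interaction, alpha .05):

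| rho | lambda at N = 36 | Power at 36 | N in equal thirds for .80 |
|---|---|---|---|
| 0 | 4.5 | .43 | 81 |
| .3 | 6.43 | .57 | 60 |
| .4 | 7.5 | .64 | 51 |
| .5 | 9.0 | .73 | 42 |
| .6 | 11.25 | .83 | 36 |
| .7 | 15.0 | .92 | 27 |
| .88 | 37.5 | above .99 | 15 |

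The smallest equal-thirds total is exactly 36 for the time effect when rho is about .46 to .51, and for the interaction when rho is about .574 to .613.

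**Dependence on alpha.** At alpha .10 and rho .5 the interaction has power .830 at 36 and .796 at 33, so 36 is again the smallest equal-thirds total.

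**A single-df contrast.** Suppose the whole group x assessment effect lies between the waitlist and the two exposure groups together. The exposure-versus-waitlist x assessment contrast in the same three-group model then carries the same lambda of 9.0 on F(1,33), and its power at 36 is .829.

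**The case against.** A reader might infer that the sponsor powered the wrong effect and that the trial is underpowered for Hypothesis 1. The documents do not support either statement without conditions.

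- **Source of the 36.** No alpha, correlation or effect is stated. The match to the time effect singles it out only if alpha .05 and correlation .5 were used. A correlation of about .574 to .613, or alpha .10 with correlation .5, gives 36 for the interaction itself. That the figure came from the time effect is a plausible inference, not a documented fact.
- **Direction of the error.** The one correlation given, .88 for the DFS, would put interaction power above .99. It is a test-retest reliability for one outcome, not a pre-post correlation under treatment. It also cannot have produced the 36, since 15 would then suffice. But it means that a shortfall on the DFS is not shown. For the DBAT outcomes no correlation is given, and one below .5 would make the shortfall larger.
- **The hypothesis's own contrast.** Hypothesis 1 compares exposure with control, and by week two both exposure groups have been assigned both video perspectives. A single-df contrast would have about .83 at 36 under the same assumptions. This is a good point, but the SAP plans the three-group ANOVA and names no such contrast, so the plan cannot yet claim that power.

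What stands is that the only power figure in the plan is not tied to the test of Hypothesis 1, and that at common default inputs it does not fit that test.

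**Conclusion.** The concern holds conditionally. Assuming f = .25 in the default metric, alpha .05, correlation .5 and equal thirds, 36 participants give .83 for the time main effect, which does not address Hypothesis 1, and about .73 for the group x assessment interaction, which needs 42 for .80. Under other values of the unstated inputs, interaction power at 36 runs from .43 (correlation 0) to above .99 (correlation .88). The firm finding is that the sample-size statement cannot be checked against the test it is meant to support. This should be corrected, but it is not a must-fix: neither the design nor the enrolment has to change.

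**What to change.** 1. **Protocol, Participants.** Redo the calculation for the group x assessment term and restate the result with the sponsor's own alpha, correlation between assessments (for each outcome, DFS and DBAT) and effect-size option. If the inputs were alpha .05 and correlation .5, the sentence should say that 36 participants give power .73 for the interaction and that .80 needs 42. The .5 used here is an assumption of this review and should not be entered as the sponsor's value unless it was.
2. **SAP, Proposed Analyses.** Name the group x assessment term as the test of Hypothesis 1.
3. **Alternative.** Pre-specify the single-df exposure-versus-waitlist x assessment contrast as the test of Hypothesis 1, and state its power. This is about .83 at 36 under the same assumptions, provided the effect is waitlist versus exposure.

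The cost is about one sentence in each document. No added enrolment is required. The downside is that the stated power may become less favourable.

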## **Apparatus**

**Physiological Data Acquisition.** A computer installed with DATAQ data acquisition recording software controls a Coulbourn Instrument no. S75-01 High Gain Bioamplifier/Coupler in order to filter and amplify electrocardiogram (ECG) data, which is used to obtain heart-rate. A Schmitt trigger apparatus, including a #551-12 Dual Retriggerable One-Shot and CI #S21-06 Bipolar Comparator, will be used to detect an R wave during recording of ECG data. Participants will have three Ag/AgCl electrodes attached: one below the right clavicle, one below the left clavicle, and one on the left torso (i.e., below the rib cage) as a ground. The electrodes are equipped with adhesive ends and are filled with a NaCl .05 molar solution. Beats per minute (bpm) are transformed from the recorded interbeat intervals.

**Access to exposure materials.** The self-directed exposure will be provided to the participants via Qualtrics, which is an online website designed to conduct research. Qualtrics is available to use on mobile devices, which will be utilized by the researchers. The participants will be given an ID and password to log into Qualtrics, and the assigned IDs will be used to differentiate the participants. Before and after each exposure video, the participants will rate distress on the Subjective Units of Distress Scale (SUDS; Wolpe, 1973). Participants will complete the SUDS on their mobile phones that will be accessing the Qualtrics website. The rating of SUDS and participants' total time spent on each webpage will be collected and stored on Qualtrics, which will be available for the researcher to download at a later time. Participants will receive daily text messages as a reminder to conduct the exposure session.

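### Question 1 asks about mobile-phone use, but no device variable is named, and the adherence measure neither requires a phone session nor defines a counted viewing

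*Protocol*

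**What the plan says.** - **Question.** The opening section of the protocol asks "whether phobic individuals will use a mobile phone in self-directed exposure therapy".
- **Analysis.** The SAP (Proposed Analyses) states: "Rates of procedure adherence (i.e., watching the video at least three times daily) will be assessed in order to examine the study's first question". It plans no other analysis for this question.
- **Platform and access.** Under Apparatus, Access to exposure materials, the exposure is delivered "via Qualtrics, which is an online website designed to conduct research". On access: "The participants will be given an ID and password to log into Qualtrics, and the assigned IDs will be used to differentiate the participants".
- **Stored data.** The same section says: "The rating of SUDS and participants' total time spent on each webpage will be collected and stored on Qualtrics".
- **Phone use.** The same section says: "Participants will complete the SUDS on their mobile phones that will be accessing the Qualtrics website". The Procedure section also asks participants to sign in daily by phone, and it describes a demonstration on the participant's own phone. The Participants section makes owning or having access to a phone an inclusion criterion.
- **Viewing.** Under Procedure, the video lasts 15 minutes, with a SUDS rating before and after it. The SUDS entry under Self-Report Measures speaks instead of a rating after each video segment.

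**The concern.** Question 1 has two parts: that the exposure was done, and that it was done on a phone. The adherence measure covers only the first. The protocol tells participants to use their phones, but whether they do so is what the question asks, so the measure cannot take it for granted. A website opened with an ID and password can be reached from other devices unless something prevents it, and the documents describe no restriction or check. The ID identifies the person, not the device.

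The SAP also gives no rule for turning SUDS ratings and page times into a viewing. Two analysts could count the same log differently.

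The adherence rate is the only planned answer to the study's first question. If it includes sessions on computers, or sessions too short to hold the video, the study could report more phone-based exposure than took place. If device type is not recorded during the study, the analysis cannot separate those sessions later.

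**Working it through.** The plan states no adherence figure, so there is none to reproduce. Its one calculated design figure, the total sample of 36, has no bearing on this point. The check sets what Question 1 needs against what the documents provide.

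| Needed for Question 1 | Named in the documents | Gap |
|---|---|---|
| Session was on a phone | Instruction, demonstration, text reminder with link | No device variable, no restriction, no check |
| Video page was open long enough | Time per webpage | Stored, but the SAP sets no threshold |
| Procedure was finished | Post-video SUDS | Stored, but not part of the adherence definition |
| Video was played and attended to | Nothing direct | Cannot be fully closed with these data |

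**Device.** Let A be the number of sessions counted as adherent and B the number of those on another device. Phone sessions number A − B, with B ≥ 0. Counting all of A can therefore only overstate phone use. The documents give no information on B.

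**What page time can do.** At normal speed a full viewing needs at least 15 minutes of page time. Three viewings need 3 × 15 = 45 minutes a day. Over 14 days that is 45 × 14 = 630 minutes, or 10.5 hours. A participant who goes straight to the post-video rating still leaves a pre/post SUDS pair, but with a short page time, so the skip can be seen. The check works in one direction only: under 15 minutes rules out a full viewing, while 15 minutes or more shows only that the page was open.

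**Illustration, on assumed inputs only.** Suppose each of exactly three daily viewings is logged with probability 0.80, independently. The logged rate of three a day is 0.80³ = 0.512, or 51%.

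- If a share q of logged viewings is off-phone, independently from session to session, the phone-only rate is (0.80 × (1 − q))³. For q = 5%, 10% and 20% this gives 44%, 37% and 26%.
- If instead a share h of participants always uses another device and otherwise behaves like the rest, the phone-only rate is 0.512 × (1 − h). For h = 10% and 20% this gives 46% and 41%.

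The gap between the two sets shows how much depends on the error pattern. Device choice is more plausibly a stable habit, which favours the second set. The protocol also allows up to five viewings a day, so a spare viewing could replace an invalid one and make the drop smaller. None of these figures is an estimate for this trial.

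**The case against.** The strongest reply is that phone use is built into the procedure. Phone access is an entry criterion, the demonstration is done on the participant's phone, reminders arrive by text, and participants are asked to follow the link and sign in by phone. Nothing in the documents suggests that computer use would be common. This stands as a reason to expect a small error. It does not remove the point, because an instruction is not a measurement of whether it was followed.

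A second reply is that this is a descriptive feasibility rate. Both hypotheses are tested on DFS, DBAT and presence scores, which do not use it. That is correct: the hypothesis tests are unaffected.

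A reader might infer two stronger points that the documents do not support:

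- *That the stored data say nothing about whether the video was played.* Page time already exposes click-through sessions. Only a page left open and unplayed escapes, and no rule based on page time would catch it.
- *That nothing else is stored, so the device can never be recovered.* The Apparatus section lists what will be kept but does not say that the list is complete. The platform may log more; the documents do not say.

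**Conclusion.** The point holds in a limited form. As written, the adherence measure does not distinguish phone sessions from others, although phone use is the subject of Question 1. Any off-phone session would push the apparent rate upward. The size is unknown and may be small, and the percentages in the illustration should not be quoted as likely effects. On viewing, the gap is a missing counting rule for data already collected, plus a residual that page time cannot resolve.

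The conclusion assumes that the documents describe all intended access controls and device checks. If the platform already records device type, the remaining gap is that the SAP does not use it.

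The change is worth making before launch, because device type may not be recoverable if it is not recorded at the time.

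**What to change.** 1. **Device.** Before launch, record device type for every session, by platform log or, if the platform cannot do this, by one self-report item per session. State the variable in the protocol. For Question 1, count only phone sessions towards adherence, and report other-device sessions separately.
2. **Counted viewing.** Define it in the SAP: total video-page time of at least 15 minutes, summed over segments if the video is split across pages, and a submitted post-video SUDS. Report shorter or unfinished sessions as a separate count.
3. **No timed button.** Do not hide the button that leads on from the video page until 15 minutes have passed. Participants who skip the video but stay to the rating would then log a full page time, which would mask behaviour that page time now shows.

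The cost is one added variable and a short SAP definition; page time and SUDS are already collected. The reported adherence rate may be lower, a self-report item adds a small burden, and page time still cannot prove attention.
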